In case of occurrence of any Adverse Event or Adverse Device Effect the appropriate form provided by 3M has to be filled in by the investigator. In case of any near incident or any event that could lead or led to any medical hazard for the investigator (user) of the investigational device the Incident/Near Incident form provided by the sponsor has to be filled in by the investigator.

Any adverse reactions to the treatment provided as part of the study will be fully investigated and recorded on the Adverse Event/Adverse Device Effect form (See Appendix), including details of the appropriate clinical action taken. An adverse event is defined as any unintended adverse experience associated with the study materials or study procedures that results in an unplanned medical assessment or treatment or changes the risk to subjects.

Restoration Failures

If a crown or onlay fails during the term of the study, the investigator will provide complete information on the manner of the failure and the proposed resolution to the study contact person at 3M. Failures associated with the bonding agent, cement, crowns and onlays that may be expected in this study include:

- loosening or complete loss of the crown or onlay

- fracture and/or chipping of the crown or onlay
- surface roughening or discoloration of the crown or onlay

Upon a determination that the crown or onlay failure did not result from other identifiable causes, and with 3M's prior approval, the Institution will make arrangements to replace the crown or onlay or carry out appropriate alternative treatment (i.e. replacement with a fixed or removable partial denture) at 3M's expense. 3M will not be responsible for any expenses incurred without its prior approval. If a crown or onlay fails after the term of the study, 3M will not be responsible for any costs incurred in its repair or replacement. 3M will have no responsibility for any other treatment a patient may receive during the term of the study or after the study has ended.

Monitoring

Monitoring visits will take place at the study center. During these visits, questions on the study conduct will be discussed and the study documentation will be reviewed. The study monitor will check whether the Clinical Investigation Plan was followed and whether the investigational device was applied according to the Instructions for use. The monitor will verify if appropriate patient consent is available for each patient and that it was included before enrolment.

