4. Clinically unsatisfactory (repair for prophylactic reasons)	11.4.1 Intense hypersensitivity. 11.4.2 Delayed with minor subjective symptoms. 11.4.3 No clinical detectable sensitivity. Intervention necessary but not replacement.	12. 4.1 Caries with cavitation and suspected undermining caries 12.4.2 Erosion in dentin 12.4.3 Abrasion/ abfraction in dentin. Localized and accessible can be repaired.
5. Clinically poor (replacement necessary)	11.5 Intense, acute pulpitis or non-vital tooth. Endodontic treatment is necessary, and restoration has to be replaced.	12.5 Deep caries or exposed dentine that is not accessible for repair of restoration.

3M
Health Care
EM-11-CR 19-03
University of Michigan School of Dentistry

**Adverse Event
Record**

AE# Site Number

Subject Number

Date of onset:
Year Month Day

NOTICE: Contact 3M Study Monitor ASAP if the adverse event is serious or unanticipated/unexpected.

Specify the sign or symptom of the adverse event.

Identify study material(s) used at the site of the adverse event. (check all that apply)

 Suglue-3	 ADH-19	 Scotchbond Universal Etchant	 Chairside Zirconia
 CoJet Sand	 Vitrebond Plus Light cure glass ionomer liner/base	 Epilar Deep Cure S	

Other: _____

*Severity at Onset (Check one)	Seriousness (Check one)	Anticipated / Expected (Check all that apply)	Related to Study Material (Check one)	Action Taken (Check all that apply)

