 Mild subject is aware of signs, symptoms but they are easily tolerated	 Not serious  Serious a) led to death, b) led to serious deterioration in health that either resulted in: 1) a life-threatening illness or injury, or 2) a permanent impairment of a body structure or a body function, or 3) in-patient or prolonged hospitalization, or 4) medical or surgical intervention to prevent life threatening illness or injury or permanent impairment to a body structure or a body function, c) led to fetal distress, fetal death or a congenital abnormality or birth defect.	 Anticipated / Expected defined in protocol/ Investigational Plan, Investigator's Brochure or Informed Consent form  Unanticipated / Unexpected in nature  Unanticipated / Unexpected in severity	 Not related  Unlikely  Possible  Probable  Causal relationship	 None  Study product discontinued  Withdrawn from study  Medications (describe below)  Other (describe below)
 Moderate signs, symptoms are sufficient to restrict but not prevent subject's daily activity				
 Severe subject unable to perform daily activity				

Outcome (Check one)

 Recovered	Date recovered:     
 Persistent effect (describe below)	Year Month Day
 Death (describe below)	

Describe the chronology of events, actions taken and outcome.

* From onset to outcome, did the adverse event increase in severity? Yes No

If yes, to what degree? Moderate Severe

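### The adverse event definition requires both an association with the study and a consequence, so it is narrower than the adverse event form it feeds and can leave unassociated events, even serious ones, off the record

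*Combined protocol and SAP*

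**What the plan says.** Section 7.3, in the part on the adverse event and incident forms, contains three statements that have to work together.

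- The trigger on which the investigator completes the form: "In case of occurrence of any Adverse Event or Adverse Device Effect the appropriate form provided by 3M has to be filled in".
- A recording instruction for that form: "Any adverse reactions to the treatment provided as part of the study will be fully investigated and recorded".
- The definition, which covers "any unintended adverse experience associated with the study materials or study procedures that results in an unplanned medical assessment or treatment". An associated experience that alters subjects' risk also qualifies.

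Adverse Device Effect is named in Section 7.3 but not defined anywhere.

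The Adverse Event Record in the Appendix asks for relatedness to study material on five levels (not related, unlikely, possible, probable, causal relationship). Its action-taken column includes none. Its lowest severity is mild, described as "subject is aware of signs, symptoms but they are easily tolerated". Its seriousness column lists death and hospitalization, among other outcomes. A notice at the top tells the site to contact the sponsor's study monitor as soon as possible if the adverse event is serious or unexpected.

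Section 8 specifies no analysis of adverse events.

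**The concern.** A safety form normally receives every untoward event and then sorts it by seriousness, relatedness and action. Here the definition does part of that sorting first. An event must be considered associated with the materials or procedures, and must have had a consequence, before it counts as an adverse event at all. No record is required of the events set aside at that step or of the reason for setting them aside.

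The cement and the adhesive are both new-generation products, and follow-up may run to five years. A judgement of no association made at the chairside cannot be reviewed later if no form exists. The same definition also controls urgent reporting, because the notice on the form applies to adverse events. A hospitalization judged unassociated is not an adverse event under Section 7.3, so neither the form nor the notice is triggered.

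**Working it through.** No arithmetic applies: the point depends on no sample size, event rate or alpha. The check takes each kind of event through the Section 7.3 text and then to the form.

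| Event | Meets the Section 7.3 definition? | Result |
|---|---|---|
| Associated with a material, leads to an unplanned visit or treatment | Yes | Recorded and graded |
| Associated with a procedure but not a material, with a consequence | Yes | Recorded; not related is a proper answer, because the form asks about material only |
| Associated, assessed at an unplanned visit, no treatment needed | Yes, an assessment is enough | Recorded; action none is a proper answer |
| Associated, mild, no unplanned assessment or treatment, risk unchanged | No | Not an adverse event; but recordable under the preceding sentence if it is a reaction to the treatment |
| Judged unassociated, not serious, treated | No | No form required |
| Judged unassociated, serious | No | No form required, no notice to the monitor |

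Four things follow.

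1. The last two rows are a real gap in the definition. The fourth row is a contradiction between two adjacent sentences, one with a consequence condition and one without.
2. Not related and none can both be used, but only within the subset that has already passed the definition.
3. The definition covers materials or procedures, while the relatedness column covers material only. A procedure-related event has no place on the form where that relation is graded.
4. With no definition of Adverse Device Effect, and with adverse events already required to be study-associated, the text gives no rule for telling the two apart.

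The other collection routes were then checked to see whether they close the gap.

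- Telephone calls (Section 7.1) record sensitivity weekly for four weeks or until the restoration is asymptomatic. They do not cover other events or later ones.
- Clinical evaluations (Section 7.2) score FDI criteria, gingival index and plaque index at baseline, six months and one, two and three years, with years four and five only if feasible. They show the state of the tooth and gingiva on the day, not the onset, seriousness, attribution or outcome of an event between visits.
- Failure reporting (Section 7.3) goes to the sponsor by its own route. The listed examples are loosening or loss, fracture or chipping, and roughening or discoloration. None is a pulpal or soft-tissue event.
- The incident form (Section 7.3) concerns near incidents, which are not defined, and hazards to the investigator as user of the device.
- Withdrawal reasons are recorded (Section 6.2), which helps only when the event ends participation.
- Monitoring (Section 7.3) checks completed forms and compares certain data with patient files. An event outside the definition generates no form to check.

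None of these records unassociated events in general.

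**The case against.** The strongest reply is that the documents are less restrictive than they first appear, and much of it stands.

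- A reader might infer that not related and none are dead options on the form. They are not: procedure-associated events can properly be unrelated to material, and an unplanned assessment without treatment, or a changed risk alone, meets the definition. Mild is severity at onset, and a mild event can still prompt a visit.
- A reader might infer that the investigator must make a causal judgement before recording anything. The text says associated, without defining it. Causal is the natural reading, particularly beside the sentence on reactions to the treatment, but a temporal reading is possible. The documents do not state a causality screen in terms.
- A reader might infer that pulpal, gingival or sensitivity events would be lost for good. The calls, FDI item 11 on sensitivity and vitality, FDI item 10 on the patient's view and the gingival index collect much of this, whatever the cause and whether or not treatment was given. What can be missed is mainly the transient event between visits.
- A reader might infer that the sponsor sees only pre-selected information. Failures reach the sponsor separately, and the monitor sees some source data.

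One part of the reply does not stand: that only a wording clarification is needed. Even on the generous reading of each item above, no provision requires a record of an event considered unassociated, serious or not.

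**Conclusion.** The concern holds in this form: the Section 7.3 definition is narrower than the form's own options imply, conflicts with the sentence before it, and leaves Adverse Device Effect undefined. Unassociated events, including serious ones, and mild events without consequence can go unrecorded before relatedness is graded.

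The size cannot be given. The documents state no expected event rates, and the missed events would by construction leave no form. The effect is on the completeness of the safety record. The Kaplan-Meier estimate of restoration survival does not use adverse event data and is unaffected.

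The conclusion assumes that the definition is applied as written and that associated is read as a judgement about the study's role. On a purely temporal reading fewer events would be excluded, but the consequence condition and the conflict between the two sentences would remain. The change should be made because it is cheap and because unrecorded events would be hard to reconstruct later.

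**What to change.** 1. Define an adverse event as any untoward medical or oral event in a subject from the start of the restorative procedure to the end of that subject's follow-up, whether or not related and whether or not it led to assessment or treatment. Starting at the procedure, rather than after placement, keeps events during anaesthesia, preparation and cementation.
2. Define an adverse device effect as an adverse event graded possible, probable or causal on the form's existing scale for study material.
3. Extend the relatedness field so that relatedness to study procedures is graded as well.
4. Align the sentence on adverse reactions with the new definition.
5. Record all serious events. If non-serious reporting is limited to reduce burden, keep all oral events and any suspected reaction to study materials or procedures wherever in the body it occurs. Limiting it to the study tooth and adjacent tissues could drop allergic or remote reactions that the current definition covers.

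The cost is revised definition text, one added field on the form and eCRF, and an amendment approved by the investigator, the sponsor and the IRB. The site would complete somewhat more forms, from 60 patients.

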Chairside CAD/CAM restorations are generally delivered with adhesive resin cements. The cement may or not require pre-treatment of the tooth by etching or a bonding agent. This creates potential confusion for a clinician as to what the optimal material selection and treatment process should be. A new adhesive resin cement (Suglue 3/3M) is the latest generation of dual cured resin cements from 3M with the innovation to use different tooth pre-treatment options, self-etch, selective enamel etch, or total etch depending on the type of restoration. This simplifies the selection process for delivery of restorations by minimizing the amount of different materials required.

This investigation will be a longitudinal clinical trial to study the long-term clinical performance of a new adhesive resin cement for chairside CAD/CAM restorations. Lithium disilicate chairside CAD/CAM onlays (IPS emaxCAD/Ivoclar) will be adhesively bonded using a selective enamel etch technique with a new generation universal adhesive based on Scotchbond Universal Adhesive (3M) and a new generation resin adhesive cement based on RelyX Ultimate (3M). Full contour zirconia crowns (3M Chairside Zirconia/3M) will be cemented using a self-adhesive technique with the new generation adhesive cement. All restorations may be followed up to five years of service.

5 Specific Aims

The specific aims of this project are:

1. Evaluate the short-term post-operative sensitivity associated with a self-etching resin cement for adhesive luting of chairside zirconia crowns.
2. Evaluate the short-term post-operative sensitivity associated with the adhesive luting technique for ceramic onlays using a selective enamel etch technique and a universal adhesive and dual cure resin cement.
3. Evaluate the longitudinal clinical performance of lithium disilicate ceramic onlays and full contour zirconia crowns for up to five years of clinical service, for a minimum of 3 years. The onlays and crowns will be evaluated with FDI criteria (Hickel et al., 2007 and 2010) for esthetic properties include surface luster, surface staining, margin staining, color match and translucency; functional properties include anatomical form, material fracture, retention, margin adaptation, occlusal contour and wear, and proximal contact and contour; and biological properties include post-operative sensitivity, recurrence of caries, erosion, abfraction as well as gingival index, and plaque index.

6 Research Plan: Methods and Materials

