6.1 Subjects

The patient population will be selected from current patients under clinical treatment at the University of Michigan Dental Clinics. Patients need to volunteer for the study and must sign the informed consent. Patients will be over 18 years of age, of either gender, and of any ethnic background. Each patient should have at least one carious lesion or defective restoration to be restored on a maxillary or mandibular premolar or molar. Each lesion or defective restoration should exhibit sufficient size to extend at least one-half the intercuspal width of the tooth requiring an onlay or full crown restoration. The onlays may contain between one and three cusps on the selected tooth as long as an occlusal margin will be present. All teeth will test vital and be asymptomatic at the beginning of treatment. No more than two restorations will be placed per patient. If a patient presents with more than two acceptable teeth for the study, molar teeth will be included prior to premolar teeth. Exclusion criteria will include:

Devital or sensitive teeth

Teeth diagnosed with symptoms of incomplete tooth fracture

Teeth with prior endodontic treatment of any kind

Teeth with a history of direct or indirect pulp capping procedures

Subjects with uncontrolled bruxism or parafunctional habits

Subject has known allergies to any product used during this study

Subject will not be available for the study duration of 5 years

Subjects with significant untreated dental disease to include periodontitis and rampant caries

Pregnant or lactating women

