6.2 Informed Consent

The Health Sciences Institutional Review Board of the University of Michigan must review and approve the investigation protocol. Patients can be recruited to the study as soon as the contract is finalized, and funding is provided. Patients who are eligible for the study will be screened by the Clinical Research Coordinator and fully informed of the nature of the study and the need for long-term availability. Each patient who participates in the study will sign an informed consent agreement and the originals will remain at the University. (A copy is included in the Appendix). [REDACTED]

[figure not shown]
[REDACTED] Patients will also receive free bitewing radiographs at the three-year recall appointment as part of routine, standard of care for monitoring dental restorations. Specific study data is not dependent on the radiographs.

After admission to the study a subject may withdraw at any time for any reason. The right of each subject to withdraw and the right of each subject to confidential treatment of personal data will be respected at all times. The PI will record any subject's withdrawal and the reason(s).

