7.2 Clinical Evaluation

Two independent evaluators will examine all restorations in the study. Clinical evaluations will be made at baseline, six months, one year, two years and three years. If feasible, subjects will return for additional follow-up visits at four and five years. Evaluation criteria are based on FDI criteria (Hickel et al., 2007 and 2010) for esthetic properties include surface luster, surface staining, margin staining, color match and translucency; functional properties include anatomical form, material fracture, retention, margin adaptation, occlusal contour and wear, and proximal contact and contour; and biological properties include post-operative sensitivity, caries, gingival index, and plaque index (see Appendix for FDI criteria description). Disagreements in evaluations will be discussed between the evaluators and a consensus judgment will be reached and recorded for every criteria.

Intraoral digital color pictures at a 1:1.5 magnification will be taken to document pre-operative, cavity preparation, and post-operative conditions. Facial and occlusal views of the tooth will be documented for both the pre-operative and post-operative conditions.

A post-cementation quadrant digital scan will be made of each test restoration using the OmniCam. Digital files will be recorded at the baseline, 6 months, 1 year, 2 year and 3 year. Optionally also at 4- and 5-year recall visits. Bite-wing radiographs and periapical radiographs of each test tooth will be available preoperatively and at the three-year recall for routine, standard of care monitoring of the restorations.

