There will be two datasets analyzed at each recall period; (1) one dataset consisting of subjects who were enrolled up to and including that recall period, and (2) one dataset consisting of all subjects with baseline data. In the second dataset (2) primary and secondary outcome variables which are missing will be imputed using the method of last observation carried forward (LOCF), wherein the last observed values for that variable will be carried forward to all remaining timepoints.

The primary analysis for this study will be the percent of intact/surviving restorations from baseline to the end of each recall period. This will be estimated using the Kaplan-Meier method, there will be no direct comparisons within this analysis. The median survival time of a restoration will be presented alongside survival curves.

The secondary analyses for this study will relate to the FDI criteria for esthetic properties including surface luster, surface staining, margin staining, color match and translucency; functional properties including anatomical form, material fracture, retention,

margin adaptation, occlusal contour and wear, and proximal contact and contour; and biological properties including post-operative sensitivity, caries, gingival index, and plaque index (see Appendix for FDI criteria description). The FDI criteria will be assessed at each recall period versus their respective baseline scores for a particular restoration within a particular subject. FDI criteria which are measured in an ordinal-discrete manner will be assessed using the Wilcoxon-signed rank test. Criteria which are measured continuously such as PI and GI will be assessed using the student's t-test, in the event that the PI and GI scores do not appear to be Normally distributed this assessment will shift to be done using the Wilcoxon-signed rank test.

A two-sided alpha of 0.05 will be used for all comparisons. There will be no adjustments made for multiplicity.

All statistical analyses will be performed e.g. using SAS version 9.4 or above (SAS Institute, Cary, NC).

9 Project Time Line

The recruitment of patients and clinical placement of restorations will begin immediately upon approval and funding of the project. It is anticipated to take 9-12 months to recruit and place the restorations required for the study.

Protocol Amendments and Discontinuing the Study

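### Dataset 2 fills the primary survival outcome by LOCF, so a restoration lost while intact counts as surviving instead of being censored; neither dataset is named as primary

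*Combined protocol and SAP*

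**What the plan says.** Section 8 (Statistical Analysis) sets up two datasets at each recall. The first is "one dataset consisting of subjects who were enrolled up to and including that recall period", with no imputation mentioned. The second is everyone with baseline data, and there "primary and secondary outcome variables which are missing will be imputed using the method of last observation carried forward (LOCF". The filled value is not limited to the next visit, because the same sentence extends it to every later recall.

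The next paragraph makes the percentage of intact or surviving restorations the primary analysis: "This will be estimated using the Kaplan-Meier method, there will be no direct comparisons within this analysis". Analyses are separate for crowns and onlays, with 40 of each (Section 6.3). Section 8 gives no censoring rule, does not exempt survival from LOCF, and does not say which dataset carries the primary result.

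On follow-up, Section 5 plans evaluation "for up to five years of clinical service, for a minimum of 3 years". Section 7.2 fixes visits at baseline, 6 months and 1, 2 and 3 years, and adds: "If feasible, subjects will return for additional follow-up visits at four and five years". Two provisions favour retention. Section 6.1 and the Appendix list as an exclusion "Subject will not be available for the study duration of 5 years", and Section 6.2 says eligible patients will be "fully informed of the nature of the study and the need for long-term availability". No dropout rate is projected.

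**The concern.** Kaplan-Meier deals with loss to follow-up by taking a restoration out of the risk set after it was last seen. LOCF does the opposite: a restoration last recorded as intact is recorded as intact at every later recall. Observed failures are carried forward correctly, so the whole effect falls on restorations lost while intact. Time that nobody observed is counted as failure-free, which pushes survival up and shrinks its standard error.

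The survival percentage is itself the primary result, so its bias and precision are what matter even though nothing is tested. Each recall will also produce two survival percentages per restoration type, and the plan does not say which is the primary one.

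**Working it through.** **Inputs.** From the documents: 40 restorations per type (Section 6.3); visits at 0.5, 1, 2 and 3 years, with 4 and 5 optional (Section 7.2); LOCF and Kaplan-Meier (Section 8). The plan gives no survival, dropout or precision figure to reproduce. The following are therefore assumptions: exponential failure; exponential dropout to year 3, unrelated to failure; a fixed share of those remaining attending both years 4 and 5; and, in the base case, failures detected only at attended visits.

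**Direction.** Kaplan-Meier is the product over visits of (1 − dⱼ/nⱼ), where dⱼ is failures and nⱼ the number at risk. LOCF leaves each dⱼ unchanged and makes each nⱼ the same or larger, so no factor can fall. With nobody censored, the product reduces to 1 − (observed failures)/40.

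**Hand example, year 3.** 2 of 40 fail by year 1, 6 of the 38 intact then leave, and 2 of the remaining 32 fail by year 3.
- Censored: 38/40 × 30/32 = 89.1%.
- LOCF: 36/40 = 90.0%.

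**Hand example, year 5.** 4 of 40 fail by year 3, 18 of the other 36 return, and 2 of those fail by year 5.
- Censored: 0.90 × 16/18 = 80.0%, Greenwood SE 7.9 points.
- LOCF: 34/40 = 85.0%, Greenwood SE 5.6 points.

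**Expected LOCF survival.** This is 1 − Σ [S(t_prev) − S(t)] × P(attending at t). For S(3) = 0.90 and 20% dropout by year 3:

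| Visit (years) | Failing in interval | P(attending) | Failures seen |
|---|---|---|---|
| 0.5 | 0.0174 | 0.963 | 0.0168 |
| 1 | 0.0171 | 0.928 | 0.0159 |
| 2 | 0.0333 | 0.862 | 0.0287 |
| 3 | 0.0322 | 0.800 | 0.0257 |

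The failures seen sum to 0.0871, so LOCF reports 91.3% against a true 90.0%.

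Across the assumed range, with overstatement in points in brackets:

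| Setting | 10% dropout | 20% dropout | 30% dropout |
|---|---|---|---|
| Year 3, true 90% | 90.6% (+0.6) | 91.3% (+1.3) | 92.0% (+2.0) |
| Year 3, true 95% | 95.3% (+0.3) | 95.7% (+0.7) | 96.0% (+1.0) |

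| Year 5, true 83.9% (3-year survival 90%) | All remaining return | 80% return | Half return |
|---|---|---|---|
| 10% dropout by year 3 | 85.1% (+1.2) | 86.2% (+2.3) | 87.9% (+4.0) |
| 20% dropout by year 3 | 86.4% (+2.5) | 87.4% (+3.5) | 88.9% (+5.0) |

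With 3-year survival of 95%, true year-5 survival is 91.8% and the overstatement runs from 0.6 points (10% dropout, all return) to 2.6 points (20% dropout, half return). A simulation of 20,000 trials with n = 40 agreed with these formulas to within 0.1 point, and LOCF was at or above censored Kaplan-Meier in every trial.

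**If failures among non-attenders are reported.** Year 3, true 90.0%, 20% dropout:

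| Share of such failures reported | LOCF | Intact non-attenders censored at last visit |
|---|---|---|
| None | 91.3% | 90.0% |
| Half | 90.6% | 89.3% |
| All | 90.0% | 88.7% |

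Censoring is therefore too low if failures are picked up after patients leave but intact restorations are not.

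**Dataset 1.** If its wording means that earlier leavers are dropped, their event-free time is lost. With true survival of 90% and 20% dropout, it gives 89.2%, an error in the other direction.

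**The case against.** The strongest reply has five parts.

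- **The mechanism is not spelled out.** Section 8 never says how imputed visit status becomes an event time, and naming Kaplan-Meier may lead a programmer to censor anyway. That is possible, but it would depart from an instruction that expressly covers primary variables.
- **The year-3 effect is small.** At 90% survival with n = 40 the standard error is √(0.9 × 0.1/40) = 4.7 points, and one restoration is 2.5 points. A bias of 0.6 to 2.0 points is below both, and no success threshold depends on it. This stands, and it limits the weight of the point.
- **The year-5 extremes stack assumptions.** They need half of those remaining to miss both optional visits despite the 5-year availability criterion, and they need an optional visit not held to count as a missing timepoint, which the plan does not settle. The half-return figures should be read as extremes.
- **Failures may reach the investigator anyway.** Subjects are existing patients of the same clinics (Section 6.1), and Section 7.3 asks for failures during the study to be reported without tying this to a recall. If every such failure is reported, LOCF is unbiased and last-visit censoring is too low. This stands, and the remedy has to deal with it.
- **Dataset 1 is unimputed and would show a divergence.** Only in part: as worded it may not be a valid censored analysis either, so nothing in the plan is clearly a standard analysis of all placed restorations.

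**Conclusion.** The concern holds. Followed literally, Section 8 removes censoring from the primary estimate in dataset 2, and the plan neither states a censoring rule nor says which dataset is primary. The result can only equal or exceed the censored estimate from the same data, and its standard error is too small.

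Under the base-case assumptions above, the bias is minor at year 3 and grows at years 4 and 5, where attendance is optional. It disappears with full retention or no later failures, and shrinks as more failures among non-attenders are reported. Every failure, dropout, return and reporting rate used here is an assumption. The missing rules are a matter of text and do not depend on those rates.

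**What to change.** - **Remove LOCF for survival.** Name one primary dataset: all placed restorations, by type, with time from placement to failure and censoring at the last evaluation at which the restoration was seen to survive.
- **Keep observed failures.** State that a failure stays in the analysis after the patient leaves or the restoration is replaced.
- **Set one rule for failures reported by patients who have stopped attending.** Count them in the primary analysis only if the status of all non-attenders is sought in the same way at that recall, for example by telephone, with intact restorations censored at that contact. Otherwise show them in a sensitivity analysis.
- **State which listed failures in Section 7.3 end survival.** That list runs from complete loss to discoloration, and time to failure needs a single event definition.

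**Cost.** SAP wording and simple programming, through the Amendment Form with approval by the principal investigator, the sponsor and the IRB. Evaluations and failures are already recorded. A telephone status check, if chosen, would be a new procedure of one call per missed recall, because the calls in Section 7.1 cover only the first four weeks. Reported survival may be slightly lower and its interval wider.
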